To address this gap, we propose to develop an intervention that specifically targets fatigue and associated psychosocial symptoms. Bounce Back Now (BBN)¹³, an existing technology-enhanced, self-management mHealth intervention designed to address disaster survivors' psychosocial health needs using a smartphone-formatted approach, will be tailored and adapted for caregivers of children with food allergy(ies), hence the renaming to **Food Allergy Symptom Self-Management with Technology (FASST)** for caregivers. Over the course of 6-months, we will conduct preliminary feasibility testing of FASST in a 4-week small randomized trial of 30 caregivers of children \leq 18 years-of-age who are newly diagnosed (\leq 90 days from diagnosis) with food allergy(ies).

Aim 1a: Perform key informant interviews (n = 10) and analyze via conventional content analysis to determine ways to improve app acceptability.

Aim 1b: Adapt FASST using data collected during key informant interviews.

Aim 2: Conduct preliminary testing of implementation processes including feasibility, acceptability, adherence and satisfaction using the RE-AIM framework with process measures, surveys, and key informant interviews in 30 caregivers randomized to receive FASST (n = 20) or the control condition (i.e., basic app with resource links) (n = 10).

Aim 3: Obtain estimates of variability and measure caregiver experienced fatigue, anxiety, depression, sleep, self-efficacy, and quality of life at baseline, 4-week intervention completion and 3-months post intervention.

B. Significance

B1. Food allergy is a highly complex condition and is growing in frequency and severity among children, negatively affecting quality of life.

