Feasibility processes (Aim 2): For the feasibility trial, we will collect multiple measures informed by the RE-AIM framework to assess feasibility and inform future efficacy and effectiveness trials. Variables will include those pertaining to the study procedures as well as participant variables. Data to be collected are described in Table 1. Specifically, 95% confidence intervals for proportions will be used to estimate dichotomous outcomes including the proportion of caregivers who agree to participate out of the number approached, the proportion adherent to the intervention protocol, i.e. providing daily symptom monitoring/tracking, using the education component, etc. For the continuous feasibility measures (e.g., patient satisfaction scores from patient surveys and end-of-study interview), frequency distributions and the median and mean responses (with 95% confidence intervals) will be obtained.

Outcome measures and estimates of variability (Aim 3): Demographic and clinical variables obtained at baseline will be described via measures of central tendency (mean, median), variability and frequency distributions as appropriate. Additionally, demographic and clinical characteristics for those who adhered to the study protocol (study completers) versus those who did not adhere (non-adherers and drop-outs) will be compared to better describe the population for this study. For continuous measures for the caregiver (fatigue, anxiety, depression, quality of life, sleep disturbance, pain and self-efficacy), the difference between pre and post intervention measurements will be estimated via 95% confidence intervals.

Post-intervention qualitative analyses (Aim 2): Data collected from post-intervention key informant interviews will be analyzed using directed content analysis³⁰ and nVivo qualitative data analysis software version 10.³¹ Consistent with the directed content analysis approach, initial coding categories are identified according to the guiding theoretical model, and for this study, will reflect the RE-AIM domains.

D3.8. Timeline

Activity	Y1Q1	Y1Q2	Y1Q3	Y1Q4	Y2Q1	Y2Q2
Organization, IRB approval						
Adaptation of BBN to FASST						
Interviews with caregivers and providers						
Analysis of interview data						
Tailoring of FASST						
Recruitment						
Intervention delivery (with assessments)						
3-month follow up assessments						
Data analysis, manuscript preparation, grant submission						

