[name] PhD, Biostatiscian (BS). [name] is a Professor in the College of Nursing with a joint appointment in the Department of Biostatistics, Bioinformatics and Epidemiology (DBBE) at MUSC. [name] has served and is currently serving as a member of several NIH/NINR R01/R21 DSM Boards, and Committees. [name] will be responsible for conducting semi-annual interim analyses, generating semi-annual AE safety reports from the electronic study research database and disseminating de-identified information to the SMC. The interim data analyses will only include safety related results; analyses in regards to study outcome will not be performed. The interim AE reports will provide typology, frequency data and outcomes of all reported and documented AE in the electronic study database. With no patient contact, [name] has no apparent conflict of interests to serve in this capacity.

[name] MSc, Program Manager (PM). [name] is the P20 Progam Manager at the College of Nursing and a member of MUSC Institute of Human Values with Fellowship certification in Research Ethics. [name] has served and is currently serving as a member of several NIH/NINR R01/R21 DSM Boards and Committees, and FDA Industry Sponsored Clinical Trials. With no patient contact, [name] has no apparent conflict of interests to serve in this capacity. [name] will be responsible for the classification of all reported adverse events (AE) and for ensuring that all serious adverse events (SAE) are forwarded to the PI and SMC in real time and in compliance with MUSC IRB policies and procedures. In addition, and in conjunction with the PI, [name] will be responsible for amending the protocol in accordance with the SMC recommendations, submitting reportable SAEs and protocol deviations to MUSC IRB, and, submitting annual Progress Reports to the NIH/NINR through MUSC's OSRP. He will also be responsible for maintaining the regulatory binder, ensuring data management validation and verification of the electronic study research database, conducting monthly internal quality control audits on all participant records, notifying the PI of any deficiencies, and the

forwarding of reportable SAE to the NIH/NINR Program Official through MUSC's OSRP within 72hrs of IRB review and acknowledgement.

SECTION B. Procedures for Safety, Risk and Confidentiality

1. Monitoring Study Safety

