This study aims to test the feasibility of a multi-component, technology-based intervention to promote self-management and symptom management among caregivers of children newly diagnosed with food allergy. To our knowledge, there are no similar interventions specifically designed for this population and purpose. As such, the PI and BS will generate semi-annual qualitative interim analysis reports on a) adverse events; and b) data obtained during phone end-of-study interviews to understand issues related to the uptake, usability, and adoption of this platform among this population. We will evaluate the screening and enrollment procedures, barriers to participation and retention, including, safety, adherence, acceptability, technology problems encountered if any, and user feedback from the participants and providers. This information gained from this structured process will be used to both guide the refinement of the current protocol and to inform the design of a larger efficacy trial. Interim analysis of outcome variables (fatigue, anxiety, and quality of life) was not considered to avoid inexact inferences and increased chance of error due to few data points, as well as potential for bias if interim results were known to the investigators. Therefore, there are no planned stopping rules for this study.

Withdrawal of Subjects

Participants may voluntarily elect to withdraw their consent at any time for any or no given reason while enrolled in the study. The PI may withdraw participants from the study at any time if they decide it is in the participant's best interest, if they do not follow the investigator's instructions, and/or if they fail to maintain to contact with the researchers or attend study visits. Withdrawals of participants may also occur if there is a protocol violation or early study closure. All data gathered from withdrawn participants will be used in the analysis plan under an Intention-to-Treat (ITT) model.

Risks to Subjects

The risks associated with this intervention are not considered greater than those that patients would otherwise be exposed to when receiving normal standard of care (SOC). However, as with all studies, there are inherent risks involved with the conduct of human subject research that gathers Protected Health Information (PHI). Participants will be made aware of these risks during the Informed Consent process. Identified study risks include: Loss of privacy, emotional distress, physical discomfort, and randomization.

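### Does an interim review of feasibility data that may refine the protocol undermine the Aim 2 estimates?

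*Combined protocol and SAP*

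**What the plan says.** In Section A of the data and safety monitoring plan, the biostatistician's role carries a limit: "The interim data analyses will only include safety related results; analyses in regards to study outcome will not be performed". Section F (Interim Analysis) has the principal investigator and the biostatistician issue qualitative reports twice a year on adverse events and on "data obtained during phone end-of-study interviews to understand issues related to the uptake, usability, and adoption of this platform among this population". It continues: "We will evaluate the screening and enrollment procedures, barriers to participation and retention, including, safety, adherence, acceptability, technology problems encountered if any". The information is to be "used to both guide the refinement of the current protocol and to inform the design of a larger efficacy trial". Section F then excludes interim analysis of the outcome variables, naming fatigue, anxiety and quality of life.

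Aim 2 in the Specific Aims is to "Conduct preliminary testing of implementation processes including feasibility, acceptability, adherence and satisfaction using the RE-AIM framework". For that aim, D3.7 states that "95% confidence intervals for proportions will be used to estimate dichotomous outcomes including the proportion of caregivers who agree to participate", and it lists among these "the proportion adherent to the intervention protocol, i.e. providing daily symptom monitoring/tracking, using the education component, etc". Continuous feasibility measures get means and medians with 95% confidence intervals. D3.7 does not mention protocol version or period. On amendments, Section A makes the Program Manager, together with the principal investigator, "responsible for amending the protocol in accordance with the SMC recommendations".

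**The concern.** Two things look wrong on a first reading. The first is a contradiction. One section says interim work covers safety only. Another has the same person report on uptake, usability and adoption in the same six-monthly cycle, with adherence and acceptability evaluated as well.

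The second is the use made of that information. If reminders, instructions or recruitment steps were altered while caregivers were still being randomised, the consent, adherence and satisfaction estimates would mix people handled under different procedures. A single proportion would then describe neither version, its value would depend on when the change fell, and it would be carried into the design of the efficacy trial. Adherence to the protocol would also need a statement of which protocol was meant.

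**Working it through.** There is no stated figure to reproduce. The sample of 30 (20 FASST, 10 control) rests on pilot-study convention, with no power, effect size or precision target. The check is a comparison of the texts, a look at timing, and an illustration of size.

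**1. What each section forbids.** In Section A the safety-only phrase is followed at once by its contrast, analyses of study outcome. Section F names outcome variables that will not be analysed early. Both exclude interim efficacy analysis. They differ only on whether qualitative feasibility feedback is also seen. That feedback is openly reviewed elsewhere: Table 1 lists weekly team meetings as a source for recruitment, adherence and technology data; Section B (Data Monitoring) puts recruitment, retention and deviations on the agenda of study team meetings; and Section B (Participant Screening and Enrollment) sends accrual and attrition reports to the safety committee.

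**2. When a report could prompt a change.** The Specific Aims place feasibility testing within 6 months. The intervention lasts 4 weeks (about 1 month), with follow-up 3 months later.
- If the 6 months include follow-up, the last participant starts by about month 6 − 1 − 3 = 2.
- If they do not, the last participant starts by about month 6 − 1 = 5.
- If the six-monthly clock starts with the randomised phase, the first report comes at about month 6, after enrolment closes on either reading.

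Two facts limit this. The clock may start with enrolment for the Aim 1 interviews, and the timeline in D3.8 spans six quarters. A change during randomisation prompted by a report is therefore uncertain, though not excluded.

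**3. What pooling would do.** Assume, for illustration only, adherence of 50% before a change and 80% after it in the FASST arm (n = 20). The expected pooled proportion is [n₁ × 0.5 + (20 − n₁) × 0.8] / 20, where n₁ is the number treated before the change.
- n₁ = 5: (2.5 + 12) / 20 = 72.5%
- n₁ = 10: (5 + 8) / 20 = 65%
- n₁ = 15: (7.5 + 4) / 20 = 57.5%

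**4. What splitting by version would give.** Exact (Clopper-Pearson) 95% intervals:

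| Adherent | Interval |
|---|---|
| 10/20 | 27.2% to 72.8% |
| 5/10 | 18.7% to 81.3% |
| 16/20 | 56.3% to 94.3% |
| 8/10 | 44.4% to 97.5% |
| 12/15 | 51.9% to 95.7% |
| 4/5 | 28.4% to 99.5% |

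The normal half-width at 50%, 1.96 × √(0.25/n), is 21.9 points for n = 20 and 31.0 points for n = 10. Under the assumed 50% and 80% with 10 participants in each period, a two-sided 5% comparison of proportions would have power of about 28%. The movement in step 3 (57.5% to 72.5%, 15 points) is well inside the interval for all 20 participants, which is about 38 points wide at 16/20. The intervals by version overlap almost entirely.

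**5. What would be on record.** The amendment route is in Section A. The approved protocol is held in the regulatory file (Section B, Binders). Protocol deviations are reportable to the ethics board (Section C.4). The date of a formal amendment, and so the participants enrolled after it, could be recovered.

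**The case for a change.** The best case for a change runs as follows. The word limiting interim work to safety is plain, and reading study outcome as the Aim 3 scales does not explain it away. Calling the reports qualitative does not help much either, because adherence is counted in days and log-ins. Section F names the running protocol separately from the later trial, so refinement cannot mean only the next study. The stated amendment route runs on recommendations from a safety committee, which does not obviously cover changes prompted by feasibility findings. Weekly meetings mean that the team could act before any six-monthly report. The Dissemination Plan also intends to present interim results without saying which. The remedy would cost only a few sentences.

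Some of this stands. The wording does not match, D3.7 has no rule for a mid-course change, and a small adjustment agreed at a weekly meeting might leave less trace than a formal amendment. The consequence does not follow. No section commits to any change, and learning from early users is a legitimate purpose of a feasibility study. Nothing in D3.7 prevents the team from reporting a change beside the overall estimate, as pilot reports normally do. As for presentations, Sections A and F already rule out interim outcome analyses, so no outcome comparison by arm should exist to be shown.

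**Conclusion.** The inconsistency between Sections A and F is a slip in wording. Settling it either way leaves every planned Aim 2 and Aim 3 analysis as it is. The missing before-and-after rule concerns an event that the documents do not plan, and analysts would handle it sensibly by reporting the change and its date. A prespecified split would gain little: with 20 FASST participants, halves of 10 give intervals more than 50 points wide (8/10: 44.4% to 97.5%), and a group of 5 gives about 71 points (4/5: 28.4% to 99.5%).

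No hypothesis test, error rate or stated precision is affected. This conclusion assumes that outcome data by arm stay out of interim reports, as both sections require, and that any change of substance goes through the amendment and deviation reporting already described. The adherence levels and split points used above are illustrative and do not come from the documents. No change to the plan is called for.

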	
Coping Factors
 
 • Social Support 	
allergies/food-allergy-101/symptoms-of-an-allergic-reaction-to-food
 
Medic Alert Bracelet: https://medicalalert.com
 
Video clips reviewing the proper usage of auto-injectable epinephrine
 
Epi-pen: https://www.youtube.com/watch?v=FXIqSuzzrws
 
AuviQ: https://www.youtube.com/watch?v=BhModQKXMT0
 
How To Read Food Labels:
 
https://www.foodallergy.org/life-with-food-allergies/living-well-everyday/how-to-read-food-labels
 
https://www.kidswithfoodallergies.org/page/choosing-safe-foods.aspx
 
Food Allergy and Anaphylaxis Emergency Care Plan: (English and Spanish)
 
https://www.foodallergy.org/life-with-food-allergies/food-allergy-anaphylaxis-emergency-care-plan
 
Talking with Your Child about their Food Allergy: https://www.foodallergy.org/life-with-food-allergies/newly-diagnosed/talking-to-children-about-their-food-allergy
 
Find a Support Group:
 
https://www.foodallergy.org/education-awareness/find-a-support-group
 
Laws and Regulations:
 
https://www.foodallergy.org/life-with-food-allergies/newly-diagnosed/laws-and-regulations
 
Reliable Websites:
 
www.foodallergy.org www.kidswithfoodallergy.org http://www.aaaai.org/conditions-and-treatments/allergies/food-allergies www.allergyhome.org

2. Symptom Monitoring and Tracking	
Caregiver Strain/Stress
 
 • Caregiving Demands 
Intrapsychic Factors
 
 • Self-perception 	
Daily text message will be sent to caregiver to remind him/her to log physical symptoms including:
 
Fatigue/Trouble Sleeping
 
Anxiety/Stress
 
Pain/Body Aches/Headache
 
Emotional/mood symptoms including:
 
Depressed mood
 
Overwhelm

		
Frustrated Worry
 
All symptoms will be pictorially represented by emoticons in the app to aid with participant discrimination.
 
Logged symptom trends will be graphically illustrated by the app for participant viewing.
 
The app will permit upload of physical and emotional symptom logs to study personnel.

3. Symptom Self-management	
Coping Factors
 
 • Social Support • Stress Management • Family Function 	
Based on feedback from component 2, participants will be given directed guidance related to component 3.
 
To address fatigue/trouble sleeping, participants will be directed to watch several short videos that focus on how to achieve better sleep; participate in guided imagery exercise; guided meditation.
 
Anxiety and stress will be addressed through deep breathing exercises; guided relaxation; exercises to increase mindfulness.
 
Altered emotional/mood states will be addressed through focused writing exercises within the app. For example, if a participant endorses negative emotions, they will be encouraged to log positive events/experiences and emotions to raise mood and esteem. If a caregiver endorses “worry”, they will have the option to create a worry tree to help decide what worries are controllable and what to do about them.
 
https://www.getselfhelp.co.uk/docs/worrytree.pdf

Food Allergy and Anaphylaxis Emergency Care Plan

FARE
Food Allergy Research & Education

FOOD ALLERGY & ANAPHYLAXIS EMERGENCY CARE PLAN

Name: _____ D.O.B.: _____

Allergy to: _____

Weight: _____ lbs. Asthma: Yes (higher risk for a severe reaction) No

NOTE: Do not depend on antihistamines or inhalers (bronchodilators) to treat a severe reaction. USE EPINEPHRINE.

Extremely reactive to the following allergens: _____

THEREFORE:

If checked, give epinephrine immediately if the allergen was LIKELY eaten, for ANY symptoms.
 If checked, give epinephrine immediately if the allergen was DEFINITELY eaten, even if no symptoms are apparent.

FOR ANY OF THE FOLLOWING:

SEVERE SYMPTOMS

LUNG

Shortness of breath, wheezing, repetitive cough

HEART

Pale or bluish skin, faintness, weak pulse, dizziness

THROAT

Tight or hoarse throat, trouble breathing or swallowing

MOUTH

Significant swelling of the tongue or lips

SKIN

Many hives over body, widespread redness

GUT

Repetitive vomiting, severe diarrhea

OTHER

Feeling something bad is about to happen, anxiety, confusion

OR A
COMBINATION
of symptoms
from different
body areas.

MILD SYMPTOMS

NOSE

Itchy or runny nose, sneezing

MOUTH

Itchy mouth

SKIN

A few hives, mild itch

GUT

Mild nausea or discomfort

FOR MILD SYMPTOMS FROM MORE THAN ONE SYSTEM AREA, GIVE EPINEPHRINE.

FOR MILD SYMPTOMS FROM A SINGLE SYSTEM AREA, FOLLOW THE DIRECTIONS BELOW:

1. Antihistamines may be given, if ordered by a healthcare provider.
2. Stay with the person; alert emergency contacts.
3. Watch closely for changes. If symptoms worsen, give epinephrine.

1. INJECT EPINEPHRINE IMMEDIATELY.

2. **Call 911.** Tell emergency dispatcher the person is having anaphylaxis and may need epinephrine when emergency responders arrive.
- Consider giving additional medications following epinephrine:
 - » Antihistamine
 - » Inhaler (bronchodilator) if wheezing
- Lay the person flat, raise legs and keep warm. If breathing is difficult or they are vomiting, let them sit up or lie on their side.
- If symptoms do not improve, or symptoms return, more doses of epinephrine can be given about 5 minutes or more after the last dose.
- Alert emergency contacts.
- Transport patient to ER, even if symptoms resolve. Patient should remain in ER for at least 4 hours because symptoms may return.

MEDICATIONS/DOSES

Epinephrine Brand or Generic: _____

Epinephrine Dose: 0.1 mg IM 0.15 mg IM 0.3 mg IM

Antihistamine Brand or Generic: _____

Antihistamine Dose: _____

Other (e.g., inhaler-bronchodilator if wheezing): _____

PATIENT OR PARENT/GUARDIAN AUTHORIZATION SIGNATURE

DATE

PHYSICIAN/HCP AUTHORIZATION SIGNATURE

DATE

[figure not shown]
FORM PROVIDED COURTESY OF FOOD ALLERGY RESEARCH & EDUCATION (FARE) (FOODALLERGY.ORG) 5/2018

HOW TO USE AUVI-Q® (EPINEPRHINE INJECTION, USP), KALEO

1. Remove Auvi-Q from the outer case.
2. Pull off red safety guard.
3. Place black end of Auvi-Q against the middle of the outer thigh.
4. Press firmly until you hear a click and hiss sound, and hold in place for 2 seconds.
5. Call 911 and get emergency medical help right away.

[figure not shown]
3

HOW TO USE EPIPEN® AND EPIPEN JR® (EPINEPHRINE) AUTO-INJECTOR AND EPINEPHRINE INJECTION (AUTHORIZED GENERIC OF EPIPEN®), USP AUTO-INJECTOR, MYLAN AUTO-INJECTOR, MYLAN

1. Remove the EpiPen® or EpiPen Jr® Auto-Injector from the clear carrier tube.
2. Grasp the auto-injector in your fist with the orange tip (needle end) pointing downward.
3. With your other hand, remove the blue safety release by pulling straight up.
4. Swing and push the auto-injector firmly into the middle of the outer thigh until it 'clicks'.
5. Hold firmly in place for 3 seconds (count slowly 1, 2, 3).
6. Remove and massage the injection area for 10 seconds.
7. Call 911 and get emergency medical help right away.

[figure not shown]
3

HOW TO USE IMPAX EPINEPHRINE INJECTION (AUTHORIZED GENERIC OF ADRENAClick®), USP AUTO-INJECTOR, IMPAX LABORATORIES

1. Remove epinephrine auto-injector from its protective carrying case.
2. Pull off both blue end caps: you will now see a red tip.
3. Grasp the auto-injector in your fist with the red tip pointing downward.
4. Put the red tip against the middle of the outer thigh at a 90-degree angle, perpendicular to the thigh.
5. Press down hard and hold firmly against the thigh for approximately 10 seconds.
6. Remove and massage the area for 10 seconds.
7. Call 911 and get emergency medical help right away.

5

HOW TO USE TEVA'S GENERIC EPIPEN® (EPINEPHRINE INJECTION, USP) AUTO-INJECTOR, TEVA PHARMACEUTICAL INDUSTRIES

1. Quickly twist the yellow or green cap off of the auto-injector in the direction of the "twist arrow" to remove it.
2. Grasp the auto-injector in your fist with the orange tip (needle end) pointing downward.
3. With your other hand, pull off the blue safety release.
4. Place the orange tip against the middle of the outer thigh (upper leg) at a right angle (perpendicular) to the thigh.
5. Swing and push the auto-injector firmly into the middle of the outer thigh until it 'clicks'.
6. Hold firmly in place for 3 seconds (count slowly 1, 2, 3).
7. Remove and massage the injection area for 10 seconds.
8. Call 911 and get emergency medical help right away.

5

ADMINISTRATION AND SAFETY INFORMATION FOR ALL AUTO-INJECTORS:

1. Do not put your thumb, fingers or hand over the tip of the auto-injector or inject into any body part other than mid-outer thigh. In case of accidental injection, go immediately to the nearest emergency room.
2. If administering to a young child, hold their leg firmly in place before and during injection to prevent injuries.
3. Epinephrine can be injected through clothing if needed.
4. Call 911 immediately after injection.

OTHER DIRECTIONS/INFORMATION (may self-carry epinephrine, may self-administer epinephrine, etc.):

Treat the person before calling emergency contacts. The first signs of a reaction can be mild, but symptoms can worsen quickly.

EMERGENCY CONTACTS — CALL 911

RESCUE SQUAD: _____

DOCTOR: _____ PHONE: _____

PARENT/GUARDIAN: _____ PHONE: _____

OTHER EMERGENCY CONTACTS

NAME/RELATIONSHIP: _____ PHONE: _____

NAME/RELATIONSHIP: _____ PHONE: _____

NAME/RELATIONSHIP: _____ PHONE: _____

Interview Guide for Caregivers of Children with Food Allergy(ies)

“Thanks for agreeing to help us with our study. We’d like to ask you a few questions about our program so we can continue to improve what we’re doing.”

Parent/Caregiver Questions

1. Have you used a tablet computer, iPad, the internet, or a smartphone before?
 - 1.1 [If so] How often do you use one?
 - 1.2 [If so] When you use a tablet, iPad, the internet, or a smartphone, what types of things do you use it for?
2. Have you ever used technology such as a tablet, iPad, the internet, or a smartphone to help you manage your health or your child’s health?
[if **No**, skip to 3.] If **yes**, ask:
 - 2.1 What types of activities did you do on the tablet, iPad, internet or smartphone?
 - 2.2 How helpful was it / were they? What did you like about these activities? Is there anything you didn’t like?
 - 2.3 What would make them better?
3. “Great. Thanks. Now I’d like to ask you some questions about the activities we have for our program. Remember, there are no right or wrong answers. The things that you tell us will help us improve the activities for other parents and caregivers. There are three main parts to the program.”

“The first part uses educational materials. They are located here [show them on tablet]. Experts in food allergy created them for caregivers. You can move from one page to the next, like this [show them on tablet]. Please take a few minutes to look them over. If you notice something you like or don’t like, or if something confuses you or catches your attention we would like to know about that.” [allow time for review]

 - 3.1 What do you like about them?
 - 3.2 What would make them better?
 - 3.3 Do you think these materials would be helpful to you? [if yes, How? If no, Why not?] [if needed: How could you see yourself using them to manage your child’s health?]
4. “Thank you. The second part of the tablet activities is an app that helps keep track of how caring for a child with a food allergy may impact you. The app is located here [show them on tablet]. The app allows you to track any symptoms you may experience as someone caring for a child with a food allergy. Please take a few minutes to look over this part of the app. If you notice something you like or don’t like, or if something confuses you or catches your attention we would like to know about that.” [allow time for review]
 - 4.1 What did you like about this part of the app?

